## **METHODS:**

**Overview:** We will conduct a pilot feasibility trial of 40 women Veterans of reproductive age with mental illness receiving outpatient mental health services at the VA Maryland Health Care System (VAMHCS). Participants will be randomly assigned to 1) the RLP-MH intervention or 2) control (receipt of the VA's Reproductive Life Planning Quick Guide and other written materials) after completion of the baseline assessment. The purpose of this pilot trial is to establish feasibility and acceptability of the RLP-MH and to explore its potential efficacy.

**Participants:** Forty participants will be recruited from VAMHCS outpatient mental health and women's health programs (Baltimore & Perry Point VAMCs; CBOCs). Inclusion criteria are: (1) female, 2) between 18 and 40 years of age, (3) chart diagnosis of schizophrenia or schizoaffective disorder, bipolar disorder, major depression, or PTSD, and (4) currently receiving mental health services at the recruitment site. Exclusion criteria are: (1) currently pregnant, or (2) inability to have children (e.g. infertility, hysterectomy, tubal ligation).

**Recruitment:** Recruitment will take place at outpatient clinics/programs within the VA Maryland Health Care System (VAMHCS). Potential VA participants will be identified by several methods: (1) CPRS chart review and screening via use of a partial HIPAA waiver, (2) VA clinician referrals of participants who meet inclusion criteria and who might be interested in participating, (3) Self referrals by participants who hear about the study and are interested in participating or who have participated in other MIRECC studies and have given permission to be contacted regarding future studies, (4) Self-referral via IRB approved study flyer and other advertisements. Per VA requirements, initial contact with potential veteran participants will be made in person or by letter prior to any telephone contact. Specifically, we will approach individuals before or after their VA appointments.

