#### **Procedures:**

**Baseline Assessment:** Women Veterans who consent to participate will complete a baseline assessment. Research assistants conducting the baseline interviews will be blind to the participant's condition. After the assessment is completed (~45-60 min), the Veteran will be randomized to one of the two study conditions by the study interventionist 1) the RLP-MH intervention (a RLP-MH session and 1-month follow-up phone session) or 2) the control (written materials on reproductive life planning).

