**STATISTICAL ANALYSIS PLAN:**

Overview: Consistent with the objectives of this small pilot randomized controlled trial (RCT), our primary data analysis approach will be to estimate means, proportions, and group differences with point and interval estimation (i.e. 95% confidence intervals). In the face of sample variation, a confidence interval provides a range for the "true" population value of a parameter consistent with the observed data. Further, estimates of recruitment, completion, and attrition percentages will be used to plan for a larger trial if warranted. We will estimate difference of means (and effect sizes) and proportions on outcomes to evaluate potential for efficacy as another input to the decision whether the RLP-MH intervention merits further testing. The trial will be conducted according to the "intent-to-treat" principle in that outcomes will be assessed regardless of RLP-MH attendance.

**Aim 1 - Feasibility:** We will calculate point and interval estimates of the overall recruitment percentage and the RLP-MH intervention completion percentage (defined as attending baseline visit and the one-month follow-up visit). The point estimate for overall recruitment percentage = number consented / number approached to participate in the trial. Interval estimation will be by 95% confidence intervals. The point estimate for the RLP-MH completion percentage = number completed / number randomized to the intervention. The overall and group attrition percentages

will also be estimated, = number without the 2-month assessment / number consented and randomized. Interval estimation will be by 95% confidence intervals. In addition to assessing feasibility, these estimates will also inform the planning of a subsequent confirmatory trial if warranted. Point and interval estimates will be calculated to estimate mean fidelity score to further assess feasibility.

Aim 2 – Acceptability: Acceptability of the RLP-MH intervention will be assessed quantitatively and qualitatively. Quantitatively, we will calculate point and interval estimates of our satisfaction questionnaire. Responses to open-ended acceptability questions at the post-treatment assessment will be compiled and examined for common themes.

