Aim 3 – Explore Potential Efficacy: Preliminary. Before we perform analyses, we will first check variable distributions and missing data. Despite randomization, with a smaller sample size it is possible for covariate imbalance to occur by chance. As a sensitivity analysis, when making group comparisons, if a clinically relevant covariate (e.g. age, race) significantly differs across the two conditions we will repeat the primary analysis adjusting for the covariate to assess its impact on outcome effects as a secondary analysis.

3a: For the three outcomes for this sub-aim, the Decisional Self-Efficacy, Attitudes Towards RLP, and RLP Behavioral Intentions scales we will estimate the difference in mean change from baseline to the 2-month follow-up between the RLP-MH and control groups using a simple random intercept linear mixed model. This will allow inclusion of all observed outcome data. Between-group effect sizes will be calculated as the model-estimated difference in mean change divided by baseline pooled (across interventions) raw standard deviation. A bootstrap procedure will be used for effect size interval estimation. In addition to the comparisons between groups above, we will estimate the mean change in the RLP-MH condition on the RLP Behavioral Intentions and Decisional Self-Efficacy Scales from baseline to post-intervention using a mixed model.

3b: The RLP behaviors that will be quantitatively analyzed are generally Yes/No self-report questionnaire items that will be assessed at the 2-month follow-up in both arms of the trial. For example, questions ask: (1) if they've had any patient-provider reproductive health discussions, (2) if they've sought after reproductive health information, and (3) if they've taken any steps to address their reproductive needs or goals. We will estimate the group difference in the proportion of 'Yes' responses with point and interval estimates using normal approximation. To adjust for a potential out-of-balance covariate (e.g. race) we will use logistic regression.

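### Aim 3a does not say whether the arms share a baseline mean; stating a common one is a valid, cheap precision gain for an exploratory comparison

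*Combined protocol and SAP*

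**What the plan says.** The target in the Statistical Analysis Plan, Aim 3a, is to "estimate the difference in mean change from baseline to the 2-month follow-up between the RLP-MH and control groups". The model is named by its class alone: the comparison is made "using a simple random intercept linear mixed model". The plan adds that every observed score enters the model. The effect size is the "model-estimated difference in mean change divided by baseline pooled (across interventions) raw standard deviation". On its interval, the plan says only this: "A bootstrap procedure will be used for effect size interval estimation". No fixed effects are listed.

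The only adjustment clause is in the preliminary paragraph of Aim 3. It is a sensitivity analysis that applies "if a clinically relevant covariate (e.g. age, race) significantly differs across the two conditions", and it leaves the main 3a estimate as it is.

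Baseline comes first in time. The Methods overview has participants assigned "after completion of the baseline assessment", and the Procedures section agrees: "After the assessment is completed (~45-60 min), the Veteran will be randomized to one of the two study conditions".

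The SAP overview gives the use of these estimates: to "evaluate potential for efficacy as another input to the decision whether the RLP-MH intervention merits further testing".

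**The concern.** Two models fit the Aim 3a wording. One gives each arm its own baseline mean (group, time, group-by-time). The other gives both arms one baseline mean (time, group-by-time, no group main effect). They yield different estimates and intervals from the same data.

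The first is the natural reading. It subtracts the whole observed baseline difference between arms, although randomization after baseline means that any such difference is chance. With about 20 women per arm that adds avoidable noise unless the correlation between baseline and follow-up scores is high. The plan treats interval width as its measure of adequacy, so the width is worth a sentence.

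**Working it through.** **Inputs from the documents.** 20 randomized per arm and 15% attrition (Sample size considerations), so 20 × 0.85 = 17 followed per arm; 95% intervals (SAP overview); effects in baseline-SD units (Aim 3a). The plan gives no precision figure for Aim 3a, so there is none to reproduce.

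**Assumed, not in the documents.** Correlation r between baseline and 2-month scores, .3 to .9; ratio of follow-up to baseline SD, 0.8 to 1.3; normal scores; dropout unrelated to scores; true effect 0.5 SD; a percentile bootstrap.

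**Step 1: what is open.** The immediate post-treatment assessment is given in the RLP-MH arm only, so the arms share two time points, baseline and 2 months. A random intercept for change between them needs baseline as a repeated response. That part of the model is implied. Only the constraint on the baseline means is unstated.

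**Step 2: known variances, equal SDs, 20 baseline and 17 follow-up scores per arm.**

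- Separate means: SE² = 2[(1−r²)/17 + (1−r)²/20]
- Common mean: SE² = 2(1−r²)/17

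At r = .5: 2[.75/17 + .25/20] = .1132, SE .337; and 2 × .75/17 = .0882, SE .297; ratio .88.

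**Step 3: estimated variances, by simulation.** The separate-means model is the REML random-intercept fit with t(32). The common-mean model with unstructured covariance has, when baseline is complete, the same effect estimate as ANCOVA in completers, with t(31). There were 20,000 replicates. For the bootstrap there were 1,000 trials per setting with 1,000 resamples within arm. Half-widths are separate / common; percentages may differ slightly from the printed values through rounding.

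| r | SE ratio (step 2) | t half-width | bootstrap half-width |
|---|---|---|---|
| .3 | .83 | .797 / .672 (16% narrower) | .817 / .701 (14% narrower) |
| .5 | .88 | .678 / .610 (10%) | .703 / .636 (9%) |
| .7 | .93 | .531 / .504 (5%) | .553 / .529 (4%) |
| .9 | .98 | .309 / .307 (under 1%) | .335 / .336 (no gain) |

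To match the bootstrap widths, the separate-means model would need 20 × (.817/.701)² ≈ 27 per arm at r = .3, and likewise about 24, 22 and 20 at the other values.

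**Step 4: unequal SDs, t half-widths, separate / common.**

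| SD ratio | r = .3 | .5 | .7 | .8 | .9 |
|---|---|---|---|---|---|
| 0.8 | .731 / .539 | .625 / .488 | .495 / .403 | .412 / .339 | .309 / .246 |
| 1.15 | .857 / .773 | .733 / .702 | .577 / .579 | .478 / .487 | .346 / .353 |
| 1.3 | .923 / .875 | .797 / .795 | .635 / .654 | .534 / .550 | .408 / .399 |

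The worst case is .654/.635 = 1.03, or 3% wider. The reason is that the regression slope of follow-up on baseline is r × SD ratio. At ratio 1.3 and r = .7 to .8 it is .91 to 1.04, so a plain change score, which fixes the slope at 1, is already near the best choice. At ratio 0.8 the slope stays well below 1 and the gain persists even at r = .9.

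t-interval coverage at ratios 1 to 1.3 was 94.3 to 95.3% for both models. Bootstrap coverage was about 91 to 95% for both.

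**Step 5: chance imbalance, equal SDs.** One standard error of the baseline difference is √(2/20) = 0.32 SD. With separate means it moves the estimate the opposite way by (1−r) × 0.32, that is 0.22, 0.16, 0.09 and 0.03 SD at r = .3, .5, .7 and .9.

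**The case against.** The strongest reply is that nothing here is wrong. The estimand, model class, divisor and interval method are all given, and choosing between two valid analyses for an exploratory aim in a 40-person pilot is the analyst's discretion. That stands, and it sets the level of the point.

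The size is also unanchored. The large gains need a low correlation or a follow-up SD below baseline, and the documents give neither. That stands as well.

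No test, threshold or power claim depends on Aim 3a. At an assumed effect of 0.5 SD, the average equal-SD bootstrap half-width exceeds 0.5 under both models at r = .3, .5 and .7, and is about .34 under both at r = .9. The gain does not change what a typical interval would show.

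Two technical cautions are fair. A completer ANCOVA would drop women with a baseline score only, against the stated wish to use all observed scores, so the mixed-model form is the one to adopt. A plug-in standard error with a normal quantile covered only about 93 to 94%, so any model-based interval needs a small-sample correction.

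A reader might infer three stronger things, and the documents do not support them:

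- **That the planned estimate is biased or its interval invalid.** Under randomization both forms estimate the same effect without bias.
- **That the plan is silent on how baseline is used.** Step 1 shows it is largely implied.
- **That separate baseline means are definitely planned.** That is the natural reading, but a common mean fits the same words.

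**Conclusion.** The point holds as an optional improvement. On the natural reading, Aim 3a gives up precision that the design makes available. With equal SDs and 17 of 20 followed per arm, the loss is worth recovering at r of about .3 to .5, small at .7 and negligible at .9. A follow-up SD smaller than baseline makes the gain larger and lasting. A clearly larger one can turn it into a loss of up to about 3%.

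These sizes rest on an assumed correlation, SD ratio and ignorable dropout. They also assume that separate means are intended. If a common mean is already intended, most of the gain is already there and only the wording is missing. The validity of the common mean does not rest on those assumptions. It follows from measuring baseline before randomization.

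**What to change.** State the Aim 3a between-arm model in full:

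- Baseline and 2-month scores are repeated responses, with fixed effects for time and group-by-time and no group main effect, so that the arms share one baseline mean.
- The covariance is an unstructured 2x2 matrix. The mean constraint supplies the gain; the unstructured form guards against unequal SDs.
- Any model-based interval uses a small-sample correction.
- The estimand, the use of all observed scores, the baseline-SD divisor and the bootstrap stay as planned. Each bootstrap sample resamples participants within arm and refits this model.

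The cost is one or two sentences of SAP text and a changed model statement. No new data are needed. The statistical price is one more covariance parameter (three instead of two), little or no gain at high correlation unless follow-up SD is smaller than baseline, and the possible 3% widening noted above.

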Sample size considerations: With an interval estimation approach, sample size is reflected in the precision of these estimates (i.e. the larger the sample the smaller the confidence interval widths). For example, for feasibility (Aim 1), with the proposed sample size of 20 randomized per study arm, observed intervention completion proportions in the RLP-MH group of .60, .75, and .90 would have 95% confidence intervals of (.39,.81), (.56,.94), and (.77,1.00). For potential efficacy assessed at the 2-month follow-up (Aim 3b), one assessed health behavior outcome will be "Any conversations with health provider regarding RLP or reproductive health? Yes/No". If the proportions of Yes responses to this question in the RLP-MH and control condition are, respectively, .25 and .10, .50 and .20, or .60 and .20, then the point estimates for the difference would be .15, .30, and .40, favoring RLP-MH, and the 95% confidence intervals for the differences would be (-.08,.38), (.02,.58), and (.12,.68). These calculations account for attrition equal to 15%.

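### Aim 3b: the normal-approximation interval for the difference in 'Yes' proportions covers slightly less than 95% at 17 women per arm and gives zero variance to an arm with no 'Yes' answers; a score-based interval is better and costs almost nothing

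*Combined protocol and SAP*

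**What the plan says.** The SAP overview makes interval estimation the main analysis approach, at the 95% level: "group differences with point and interval estimation (i.e. 95% confidence intervals"). The Aim 3b outcomes are "generally Yes/No self-report questionnaire items that will be assessed at the 2-month follow-up in both arms of the trial". For these items the method is named outright: the between-arm difference in 'Yes' proportions is to be reported "with point and interval estimates using normal approximation". No exact, score or adjusted interval is offered, and there is no rule for an arm with no 'Yes' answers. Logistic regression appears only as a way to adjust for an imbalanced covariate.

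Sample size considerations works "with the proposed sample size of 20 randomized per study arm". It takes 'Yes' proportions in RLP-MH and control that "are, respectively, .25 and .10, .50 and .20, or .60 and .20", and reports that "the 95% confidence intervals for the differences would be (-.08,.38), (.02,.58), and (.12,.68"). It adds: "These calculations account for attrition equal to 15" per cent.

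**The concern.** The usual normal-approximation (Wald) interval is the observed difference plus or minus 1.96 estimated standard errors. It is known to be weak when groups are small and proportions lie near 0 or 1. With 17 women per arm and control rates of .10 to .20, the expected number of control 'Yes' answers is only 17 x .10 = 1.7 to 17 x .20 = 3.4. Two faults can follow. The interval may hold the true difference less often than 95% of the time. And an arm with a proportion of exactly 0 or 1 has an estimated variance of zero, so its uncertainty drops out of the interval.

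The SAP uses differences in proportions as an input to deciding whether RLP-MH merits further testing. An interval that is too narrow overstates what a pilot of this size has shown about a behavior.

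**Working it through.** **Inputs.** 20 randomized per arm, 15% attrition and the three pairs of proportions come from Sample size considerations. The 95% level comes from the SAP overview and the method from Aim 3b. Number analysed: 20 x 0.85 = 17 per arm.

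**Which normal approximation is meant.** The unpooled form is d ± 1.96 x sqrt[p1(1-p1)/n + p2(1-p2)/n]. At n = 20:
- .25/.10: .15 ± 1.96 x .1178 = (-.08,.38)
- .50/.20: .30 ± 1.96 x .1432 = (.02,.58)
- .60/.20: .40 ± 1.96 x .1414 = (.12,.68)

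These are the printed intervals, so the unpooled Wald form is what the plan intends. They match 20 analysed per arm, not 17. At n = 17 the same formula gives (-.10,.40), (-.00,.60) and (.10,.70). That mismatch with the stated attrition is a separate matter. It is noted here only so that a change of n is not mistaken for a change of method.

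**Exact coverage at 17 per arm.** All 18 x 18 pairs of 'Yes' counts were enumerated, each weighted by its two binomial probabilities. An interval was counted as a miss above if it lay wholly above the true difference, and as a miss below if wholly below.

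| True rates | Wald coverage | Wald misses above / below | Newcombe coverage | Newcombe misses above / below |
|---|---|---|---|---|
| .25/.10 | .937 | 2.3% / 4.0% | .962 | 1.1% / 2.7% |
| .50/.20 | .931 | 4.4% / 2.5% | .946 | 1.7% / 3.7% |
| .60/.20 | .928 | 4.8% / 2.4% | .948 | 1.3% / 3.9% |

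Miettinen-Nurminen covers .957, .956 and .948. Over a grid of true rates from .05 to .95 in steps of .05, Wald coverage averages .928 (minimum .823) and Newcombe .950 (minimum .918). Analysing 20 per arm does not cure the shortfall: Wald coverage is then .936, .931 and .928.

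**Empty arms at 17 per arm.**
- Chance of no control 'Yes': .90^17 = .167 at a control rate of .10; .80^17 = .023 at .20.
- Given an empty control arm in the .25/.10 scenario, Wald coverage is .885 and Newcombe .960. At .50/.20 and .60/.20 both fall further (Wald .684 and .552, Newcombe .834 and .736), but there the event is uncommon.
- Example, 4/17 vs 0/17: Wald (.03,.44), Newcombe (.004,.473). The widths are about .40 and .47.
- Both arms empty at .25/.10: .75^17 x .90^17 = .0013, or 0.13%. Wald then gives (0,0) and Newcombe (-.18,.18).

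**Width.** Mean width at 17 per arm, Wald vs Newcombe: .480 vs .506 at .25/.10, .589 vs .556 at .50/.20, .581 vs .547 at .60/.20. Averaged over the grid: .536 vs .526.

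**The case against.** The practical effect is small. The shortfall in the plan's scenarios is 1.3 to 2.2 percentage points, the point estimate is unaffected, and the two methods disagree on whether zero is excluded in only 1.9%, 2.8% and 1.1% of trials. Aim 3 is labelled exploratory, and no test or go/no-go threshold hangs on an Aim 3b interval. All of this stands, and it limits the weight of the point. It does not defend the named method, which does worse on coverage in all three scenarios and has no rule for empty cells.

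Four stronger readings are tempting, and the documents and figures do not support them:
- *The method breaks down whenever one arm is empty.* It does not. The interval loses that arm's variance and is too narrow, but it still has width. Full collapse needs both arms empty (or both all 'Yes').
- *The error is optimistic.* That is true only of the two larger-effect scenarios. At .25/.10, where an empty control arm is most likely, the misses lean low. Newcombe is also uneven, with more misses below than above in all three scenarios.
- *A result such as 4/17 vs 0/17 would falsely exclude zero.* The Newcombe interval also excludes zero there, if only just, so this example does not separate the methods.
- *These intervals decide the future of RLP-MH.* The SAP treats the efficacy estimates as one further input beside recruitment, completion and attrition.

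**Conclusion.** The point holds as a modest but real weakness in the choice of method. At 17 per arm, the nominal 95% interval covers about 93% to 94% in the plan's own scenarios. The sparse-cell behavior is the more practical concern, because an empty control arm has about a 1 in 6 chance at the plan's control rate of .10. The (0,0) interval is rare at the plan's rates and would matter mainly for a behavior that hardly anyone reports.

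This rests on 17 analysed per arm, independent binomial responses, and the unpooled Wald form that reproduces the printed intervals. The size of the shortfall depends on the true rates: Wald coverage is .886 at .10/.05 but .969 at .10/.10.

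**What to change.** In Aim 3b, replace the normal-approximation wording with: a 95% Newcombe hybrid-score confidence interval for the difference in proportions. Miettinen-Nurminen is an acceptable alternative. Use the same method for the difference examples under Sample size considerations. At 17 per arm, with the plan's proportions entered directly, Newcombe gives about (-.12,.40), (-.02,.55) and (.07,.63). These differ from the printed intervals in both method and n. The comparison that isolates the method is with the Wald results at 17 per arm: (-.10,.40), (-.00,.60) and (.10,.70).

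The cost is one phrase in the SAP and three recalculated examples, using a method found in standard software. The downside is slightly wider intervals at low rates (mean width .506 vs .480 at .25/.10).

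### The Aim 3b example intervals do not include the 15% attrition the SAP says they include, and Aim 1 names no interval method while its worked completion intervals match only the Wald formula at n = 20

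*Combined protocol and SAP*

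**What the plan says.** The SAP overview makes point and interval estimation the main analysis approach. Under Aim 1 - Feasibility the only statement on method is "Interval estimation will be by 95% confidence intervals". The denominators are explicit: "The point estimate for the RLP-MH completion percentage = number completed / number randomized to the intervention", and for attrition "number without the 2-month assessment / number consented and randomized". The use is also stated: "these estimates will also inform the planning of a subsequent confirmatory trial if warranted".

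A method is named in one place only, Aim 3b, where the difference in Yes proportions is estimated "with point and interval estimates using normal approximation".

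Sample size considerations gives worked examples for 20 randomized per arm. Completion proportions of .60, .75 and .90 "would have 95% confidence intervals of (.39,.81), (.56,.94), and (.77,1.00"). For the Aim 3b pairs .25 v .10, .50 v .20 and .60 v .20, "the 95% confidence intervals for the differences would be (-.08,.38), (.02,.58), and (.12,.68"). The paragraph closes: "These calculations account for attrition equal to 15" percent.

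**The concern.** In a pilot planned on interval estimation, the worked intervals are the whole sample size justification.

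- **Attrition.** With 20 randomized per arm, 15% attrition leaves 17. If the Aim 3b intervals were computed at 20, the closing sentence is wrong as written and the stated precision is too good on the plan's own terms.
- **Interval method.** Aim 1 leaves the method open, and the worked completion example is the only clue to it. An upper limit of exactly 1.00 for an observed 18/20 suggests a symmetric interval that ran past 1 and was cut. With 20 people and proportions near 1 (completion) or near 0 (attrition), such intervals cover less than 95%. For completion the error tends to be optimistic: the lower limit sits too high. These are the estimates meant to inform a confirmatory trial.

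**Working it through.** **Inputs.** From Sample size considerations: 20 randomized per arm, the example proportions, the printed intervals and 15% attrition. From Aim 1: the denominator for completion and per-arm attrition is the number randomized, so n = 20 for both. From Aim 3b: normal approximation for the difference. z = 1.96.

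**Step 1. Aim 3b intervals.** Formula: (p1 - p2) ± 1.96 × √[p1(1-p1)/n + p2(1-p2)/n]. After 15% attrition, n = 20 × .85 = 17.

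| Pair | Printed | n = 20 | n = 17 |
|---|---|---|---|
| .25 v .10 | (-.08,.38) | (-.081,.381) | (-.100,.400) |
| .50 v .20 | (.02,.58) | (.019,.581) | (-.004,.604) |
| .60 v .20 | (.12,.68) | (.123,.677) | (.099,.701) |

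For the middle pair at n = 17: √[(.25 + .16)/17] = .1553, and .30 ± 1.96 × .1553 = (-.004,.604). The printed values are those for n = 20. A pooled-variance version does not rescue them: for the middle pair it gives (-.021,.621) at 17 and (.004,.596) at 20. The correct half-widths are larger by √(20/17) = 1.085, about 8.5%.

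**Step 2. Completion intervals.** Wald formula: p ± 1.96 × √[p(1-p)/n].

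| Method | 12/20 | 15/20 | 18/20 |
|---|---|---|---|
| Printed | (.39,.81) | (.56,.94) | (.77,1.00) |
| Wald, n = 20 | (.385,.815) | (.560,.940) | (.769,1.031) |
| Wald, n = 17 (same proportions) | (.367,.833) | (.544,.956) | (.757,1.043) |
| Wilson | (.387,.781) | (.531,.888) | (.699,.972) |
| Clopper-Pearson | (.361,.809) | (.509,.913) | (.683,.988) |

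Wald at n = 20 matches all three once 1.031 is cut to 1.00. Agresti-Coull, Jeffreys, a t-based interval and a continuity-corrected Wald interval were also tried; none matches all three.

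**Step 3. Coverage if Wald is used.** For each true rate, the binomial probabilities of the outcomes whose interval contains that rate were summed exactly, then averaged over an even grid of true rates.

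Completion, n = 20 (nominal coverage .950, each tail .025):

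| Method | Coverage, .60-.90 | Lower limit too high | Upper limit too low |
|---|---|---|---|
| Wald | .909 | .074 | .017 |
| Wilson | .954 | .014 | .032 |
| Clopper-Pearson | .975 | .010 | .015 |

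The size depends on the range. Over .60-.80, Wald averages .919 with the lower limit too high .061 of the time. The ratio to nominal is .074/.025 = 3.0 over the wider range and .061/.025 = 2.4 over the narrower one. At single true rates Wald covers .928 at .60, .895 at .75 and .876 at .90.

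Per-arm attrition, n = 20, averaged over true rates .10-.20: Wald .891, Wilson .957, exact .980. Overall attrition, n = 40: .918, .953, .972. At the plan's own 15%, per-arm Wald coverage is .819.

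**Step 4. The extreme outcome.** 20/20 completed gives Wald (1.00,1.00), Wilson (.839,1.00) and exact (.832,1.00). At a true rate of .90, 20/20 has probability .9^20 = .122, which is the whole optimistic miss there.

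**The case against.** The strongest reply concerns the interval method. The completion figures are an illustration in a sample size paragraph and do not specify the analysis. A reader might infer that the plan commits Aim 1 to Wald intervals. The documents do not support that: the normal approximation is named for Aim 3b only, and an exact interval at analysis would contradict nothing. The coverage loss is therefore conditional. Nor are the printed completion figures miscalculated; they are correct Wald arithmetic.

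A reader might also infer that a go/no-go decision would be distorted. The plan sets no progression threshold and no test on completion or attrition, so no stated decision changes.

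The .60 to .90 range comes from example observed proportions, not assumed true rates, and the shortfall shrinks on a narrower range. The alternatives are not free of faults: Wilson covers .935 at a true rate of .75 and its misses lean the other way, and the exact interval is conservative and wider than Wald in all three examples.

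All of this stands, and it limits the second problem to a modest one. It leaves two facts in place: the method is unnamed, and the only example follows the formula with the weakest coverage of the three in the Step 3 tables.

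The attrition mismatch is not touched by any of this. It does not depend on the choice of interval. Reading 20 as the number left after attrition fails, because the paragraph says 20 are randomized per arm. One stronger reading should be resisted: losing the exclusion of zero in the middle example does not show that the trial is too small. The proportions are hypothetical and the plan tests no hypothesis with them.

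**Conclusion.** The two problems hold separately and should not lend each other weight.

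1. **Attrition: an error as written.** The Aim 3b intervals use all 20 per arm although the text says they allow for 15% attrition. At 17 per arm the half-widths grow by about 8.5%, and the middle example includes zero. This rests only on the plan's own figures and its own approximation.
2. **Aim 1 method: an omission with a conditional cost.** If the analysis follows the worked example, average coverage is about .91 for true completion of .60-.90 (.92 for .60-.80) and .89 for per-arm attrition of .10-.20, and completion misses are mostly, not wholly, optimistic. This assumes Wald at n = 20 and true rates spread evenly over those ranges. The recruitment percentage is not assessed, because the number to be approached is not given.

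The consequence is confined to the stated precision and to planning of the later trial. It is worth correcting, but it does not threaten the pilot.

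**What to change.** - **Aim 3b examples.** Restate at 17 per arm as (-.10,.40), (-.004,.604), (.10,.70), or delete the attrition sentence. Keep three decimals in the middle example so that its sign is visible. If the sentence stays, limit it to Aim 3b, since completion is defined on all randomized.
- **Aim 1 method.** Add one sentence naming Wilson or Clopper-Pearson for completion and attrition. Restate the completion examples as (.39,.78), (.53,.89), (.70,.97) for Wilson, or (.36,.81), (.51,.91), (.68,.99) for exact.
- **Aim 3b method.** Changing it is optional. At the three example pairs with 20 per arm, exact enumeration gives the normal approximation coverage of .936, .931 and .928, a smaller shortfall than the Wald averages for completion or attrition.

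**Cost.** A sentence of text, revised example figures and a software option; no participants, data or design change. Some lower limits look less favourable: 18/20 moves from .77 to .70 (Wilson) or .68 (exact), and 15/20 from .56 to .53 or .51. At 12/20 the Wilson limit is essentially unchanged, while the exact limit falls from .39 to .36. Wilson's upper limit misses slightly more often than nominal (.032 against .025), and exact intervals over-cover (.975 on average).
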